10.2.3 Notification of deaths

There is an overall likelihood of death in all cases of severe bronchiolitis of 1-2%. All deaths that occur during the protocol-specified AE reporting period, regardless of relationship to study drug, must be recorded. All deaths should be reported on a "Serious Adverse Event CRF" and returned to the CTRC within 24 hours.

Death should be considered an outcome and not a distinct event. The event or condition that caused or contributed to the fatal outcome should be recorded as the single medical concept on the appropriate CRF; e.g. death following pneumothorax, here pneumothorax is the event. Generally, only one such event should be reported. The term "sudden death" should only be used for the occurrence of an abrupt and unexpected death due to presumed cardiac causes in a participant with or without pre-existing heart disease, within 1 hour of the onset of acute symptoms or, in the case of an unwitnessed death, within 24 hours after the participant was last seen alive and stable. If the cause of death is unknown and cannot be ascertained at the time of reporting, "unexplained death" should be recorded on the appropriate CRF. If the cause of death subsequently becomes available (e.g. after post-mortem examination), "unexplained death" should be replaced by the established cause of death.

10.3 Notes on Severity / Grading of Adverse Events

The assignment of the severity/grading should be made by the investigator responsible for the care of the participant using the definitions below.

Regardless of the classification of an AE as serious or not, its severity must be assessed according to medical criteria alone using the following categories:

Mild: does not interfere with routine activities

Moderate: interferes with routine activities

Severe: impossible to perform routine activities

A distinction is drawn between serious and severe AEs. Severity is a measure of intensity (see above) whereas seriousness is defined using the criteria in section 10.1, hence, a severe AE need not necessarily be a SAE.

IRAS 220853 Page **53** of **87**

10.4 Relationship to Trial Treatment

The assignment of the causality should be made by the investigator responsible for the care of the participant using the definitions in Table 3: Definitions of Causality. An AE for which the causal relationship to the study drug is assessed by the investigator as "possible", "probable" or "almost certain" is an AR.

If any doubt about the causality exists the local investigator should inform the CTRC who will notify the Chief Investigator (CI). In the case of discrepant views on causality between the investigator and others, the MHRA will be informed of both points of view.

Table 3: Definitions of Causality

Relationship	Description
Unrelated	There is no evidence of any causal relationship. N.B. An alternative cause for the AE should be given.
Unlikely	There is little evidence to suggest there is a causal relationship (e.g. the event did not occur within a reasonable time after administration of the trial medication). There is another reasonable explanation for the event (e.g. the participant's clinical condition, other concomitant treatment).
Possibly	There is some evidence to suggest a causal relationship (e.g. because the event occurs within a reasonable time after administration of the trial medication). However, the influence of other factors may have contributed to the event (e.g. the participant's clinical condition, other concomitant treatments).
Probably	There is evidence to suggest a causal relationship and the influence of other factors is unlikely.
Almost certainly	There is clear evidence to suggest a causal relationship and other possible contributing factors can be ruled out.

10.5 Expectedness

The Reference Safety Information (RSI) in BESS is section 4.8 (Undesirable effects) of the Curosurf® Endotracheopulmonary Instillation Suspension SPC.

It is not a regulatory requirement for a reporting physician to provide their opinion of expectedness. Therefore, the reporting physician at the local research site will not be asked to make an assessment of expectedness. The assessment of expectedness will be made by the CI (or their medically qualified delegate) using BESS's current MHRA-approved RSI following receipt of the "Serious Adverse Event CRF" at CTRC.

All events judged by the investigator to be possibly, probably, or almost certainly related to the IMP, graded as serious and unexpected (see current MHRA-approved trial RSI (Curosurf® Endotracheopulmonary Instillation Suspension SPC) for list of Expected Adverse Events) should be reported as a SUSAR.

IRAS 220853 Page **54** of **87**

10.6 Follow-up After Adverse Events

All adverse events should be followed until satisfactory resolution or until the investigator responsible for the care of the participant deems the event to be chronic or the participant to be stable.

When reporting SAEs and SUSARs the investigator responsible for the care of the participant should apply the following criteria to provide information relating to event outcomes:

- resolved;
- resolved with sequelae (specifying with additional narrative);
- not resolved/ongoing;
- on-going at final follow-up;
- fatal or unknown.

10.7 Time Period for Safety Reporting

Investigators and delegated members of the local research teams will report to CTRC on the appropriate CRFs (see section 10.8):

- all adverse events from randomisation until 24 hours after their final intervention (whether poractant alfa or placebo);
- all adverse reactions from randomisation until 90 days post-randomisation or hospital discharge (whichever is sooner).

Following these periods, site staff are not required to report any non-serious events, however any serious events (SAEs/SARs/SUSARs) which they become aware of must be reported to CTRC.

[figure not shown]
Upon becoming aware of a serious adverse event (SAE/SAR/SUSAR), the Investigator or other delegated member of the team **must** report this to the CTRC **within 24 hours**.

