8.2 Participant follow-up

Clinical follow-up (daily data collection) will take place for the period of time between randomisation and the discharge from hospital of the participant.

All non-serious adverse events will be collected until 24 hours after the participant receives their final trial intervention; please note that this may not be their third dose if less than 3 doses are required before the participant meets the criteria to be ready for weaning (see section 10 for full safety reporting information).

Non-serious adverse events occurring after 24 hours post-final intervention but before 90 days post-randomisation/discharge home/death should be reported if the local Investigator believes that they may be related to the intervention.

Although active monitoring for adverse events and adverse reactions will cease at 24 hours post final intervention and 90 days post randomisation / discharge home / death respectively, any which the site research team become aware of after these time-points which are assessed as serious (i.e. Serious Adverse Events or Serious Adverse Reactions) should be reported to the CTRC. Routinely collected audit data regarding participant care will be collected from PICANet until 90 days post randomisation.

Parent reported outcomes will be collected via the LRSQ at 6 and 12 months post randomisation for participants recruited in seasons 1 and 2, and at 6 months only for participants recruited in season 3.

The end of follow-up definition for each participant will therefore be 12 months post randomisation for participants in season 1 and 2, or 6 months post randomisation for participants in season 3.

IRAS 220853 Page **36** of **87**

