8.5 Procedures for Assessing Safety

Safety will be assessed by:

- The Principal Investigator (PI) or delegated research staff actively monitoring and reporting all adverse events from randomisation until 24 hours after the participant's last administration of poractant alfa (see section 10 for adverse event reporting).
- Limited physical examination that includes the recording of vital signs before and after each study intervention
- Routinely collected patient care data downloaded from the PICANet audit on a regular basis by each site and transferred to the CTRC
- Mortality and readmission data collected by each site at 90 days post randomisation

Participants will be actively monitored and any adverse events identified must be reported to the CTRC, whether identified from trial assessments or standard care (e.g. identified during standard daily examinations). Non-related events will be reported from randomisation to 24 hours after the participant's last administration of poractant alfa or placebo for. Adverse events occurring after this time point until 90 days post randomisation / discharge home / death will be reported if felt to be related to the intervention. Any serious events or reactions (SAEs/SARs) should be reported to CTRC regardless of the timeframe.

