8.6.2 Special Assays or Procedures

8.6.2.1 Collection & processing of BAL fluid

BAL sampling with 0.9% sodium chloride (2x1mL/kg) will be done for all participants immediately prior to intervention, at 24hrs post intervention and repeated daily while the infant remains on MV (see Table 2).

Both tracheal toilet and BAL sampling is done by catheter access to the trachea via the endotracheal suction port without disconnecting the infant from the ventilator or by disconnecting the infant from the ventilator and performing hand bagging while accessing the trachea via a side-port with one-way valve.

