# 17.4.3. Secondary Outcome 2: Number of trial interventions

This outcome will assess if there is evidence of a difference in the number of trial interventions (both poractant and placebo) given to the infants between trial arms.

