#### 20.2. Presentation of the data

All AEs reported by the clinical investigator will be presented, with separate tables for serious and non-serious events. Both the number of events and the number of patients experiencing each event will be provided. A third table will be presented grouping non-serious AEs by severity; participants will be counted in the most severe category experienced if they experienced more than one. Similarly, a fourth table will be presented grouping non-serious ARs by causality (where the relationship to intervention is recorded as possibly, probably or almost certainly) and participants will be counted in the highest relationship category experienced if they experienced more than one.

The above tables for serious and non-serious events will be repeated but will be further grouped by whether or not the patient received muscle relaxant prior to the administration of the intervention. Serious adverse reactions will be presented as line listings, detailing the description, seriousness, severity, expectedness, relationship to intervention and outcome.

Relationship to study drug will be assessed first assuming the participant is in the intervention arm, then assuming they are in the control arm, so as to avoid unnecessary unblinding. However, for the classification of causality only the relationship to the intervention received will be reported.

For all AE descriptions, MedDRA classifications will be used. Events will be reported using the preferred term, categorised by system organ class. Results will be presented descriptively; no formal statistical testing will be undertaken for interim reports.

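### Full adverse-event collection stops 24 hours after each infant's own last dose, so the length of observation can differ by arm, and SAP 20.2 compares crude counts without allowing for it

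*Protocol*

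**What the plan says.** **Window.** Protocol 10.7 asks for "all adverse events from randomisation until 24 hours after their final intervention (whether poractant alfa or placebo"). Protocol 8.2, 8.5 and Table 1 set the same limit, and SAP 8.8 repeats it.

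**What ends dosing.** Protocol 8.2 says of the final intervention that "this may not be their third dose if less than 3 doses are required before the participant meets the criteria" for weaning. Protocol 8.7.2.1 also allows withdrawal from intervention for toxicity, intercurrent illness, a change in condition or parental choice.

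**Dose count as an outcome.** SAP 17.4.3 looks for "evidence of a difference in the number of trial interventions (both poractant and placebo) given to the infants between trial arms".

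**Analysis.** The safety set is infants with at least one dose, by treatment received (SAP 20.1). In SAP 20.2, "Both the number of events and the number of patients experiencing each event will be provided", with further tables by severity, causality and muscle relaxant use. No time under observation, common window or breakdown by number of doses is specified.

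**What runs on another clock.** Protocol 10.7 also requires "all adverse reactions from randomisation until 90 days post-randomisation or hospital discharge (whichever is sooner"). On serious events, Protocol 8.5 says: "Any serious events or reactions (SAEs/SARs) should be reported to CTRC regardless of the timeframe". Protocol 8.2 nevertheless says that "active monitoring for adverse events and adverse reactions will cease at 24 hours post final intervention and 90 days post randomisation" (or discharge home or death) respectively. In Table 1, air leak runs to PICU discharge, tube replacement to successful extubation, PICU death to PICU discharge, and readmission and mortality to 90 days.

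**The concern.** The end of full collection is fixed by an event after randomisation that treatment can influence, and the trial itself tests whether the arms differ on it. If one arm stops dosing earlier, its infants are fully observed for less time. A table of counts then mixes a difference in safety with a difference in observation.

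Once the window closes, a non-serious event is reported only if the investigator thinks it may be related. Protocol 7.4 accepts that blinded carers may sometimes infer a surfactant allocation, so that judgement is not a sure substitute for collecting everything. At stake is the general adverse-event comparison, one of eight safety outcomes serving Secondary Objective 3.

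**Working it through.** **1. Window length.** The documents state no length in hours. It follows from the dose times in Protocol 8.1 plus 24 h:

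| Doses received | Last dose | Window ends | Value used below |
|---|---|---|---|
| 1 | T0 to T2 | 24-26 h | 25 h |
| 2 | T11 to T13 | 35-37 h | 36 h |
| 3 | T23 to T25 | 47-49 h | 48 h |

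A one-dose infant is fully observed for 25/48 = 52% of the time of a three-dose infant.

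**2. Effect for one infant.** Assume a constant hazard h = -ln(1 - R)/48, where R is the risk of at least one event in 48 h (assumed). A 25 h window captures 1 - exp(-25h): 5.3%, 17.0% or 38.0% for R = 10%, 30% or 60%.

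**3. Check of the ventilation model.** Protocol 11.3 gives mean durations of 4.83 and 4.08 days, both with SD 2.5. On a log-normal scale the variances are ln(1 + 0.518²) = 0.237 and ln(1 + 0.613²) = 0.319. The log means are ln(4.83) - 0.237/2 = 1.456 and ln(4.08) - 0.319/2 = 1.247, a difference of 0.209. Then n = (z for two-sided 0.05 + z for power)² × (0.237 + 0.319)/0.209², evaluated without rounding, is 99.5 for 80% power and 133.2 for 90%. These round up to the protocol's 100 and 134 per group, so the parameters are the plan's own.

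**4. Effect by arm.** The documents give no dose distribution, so it is derived from those durations. An infant has one dose if ready to wean before T12, two if ready between T12 and T24, and otherwise three. Two inputs are assumed: 0, 1 or 2 days of ventilation before randomisation (eligibility caps this at 48 h), and readiness 0, 12 or 24 h before extubation. Event hazards are identical in both arms, with R = 10%, 30% or 60%.

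The most affected of the 27 combinations (1 day ventilated, 24 h lead, R = 10%):

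- Control: 13.3%, 9.8% and 77.0% have one, two and three doses. Mean window 0.133×25 + 0.098×36 + 0.770×48 = 43.8 h.
- Surfactant: 26.9%, 11.9% and 61.2%. Mean window 0.269×25 + 0.119×36 + 0.612×48 = 40.4 h, a ratio of 0.92.
- Infants with a recorded event: 9.15% against 8.46%, a ratio of 0.925.

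The least affected (0 days, 0 h lead, R = 60%) gives mean windows of 48.0 and 47.8 h and a ratio of 0.998.

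Across all combinations the mean window is 39.8-48.0 h in control and 37.3-47.8 h with surfactant, and the ratio of infants with an event is 0.925-0.998. Equal hazards would therefore show 0 to 7.5% fewer treated infants with an event.

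**5. With a common window.** If every dosed infant is followed to T49 (24 h + 1 h grace + 24 h), observation is equal by design and the window-driven ratio is 1.00.

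**The case against.** **The gap is narrower than the rule alone suggests.** A reader might infer that all safety information stops 24 h after the last dose. It does not, given the separate limits for adverse reactions, serious events and named outcomes. What is lost is mainly non-serious events judged unrelated, plus active surveillance for serious ones. This stands.

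**Harm that stops dosing is not hidden.** A reader might infer that an infant stopped for toxicity escapes observation. An event that stops dosing has normally been recorded already, adverse events are followed to resolution (Protocol 10.6), and later related events stay reportable. Discontinuations and their reasons (SAP 14.2), doses received (SAP 17.3) and failures to administer because of an adverse event (SAP 17.5.1) are also reported. Only later events judged unrelated are lost.

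**Larger biases need invented dose splits.** Assuming 10/10/80% for one, two and three doses in control (mean 44.5 h) against 40/20/40% with surfactant (36.4 h) gives a ratio of 0.82. Nothing in the documents supports such a split. The ventilation figures give at most 7.5%. That model covers stopping for recovery only, so toxicity stops could add to it, but no figure is available.

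**Part of any difference may be real.** Protocol 3.4.2 describes transient reactions around administration, and each dose has 24 h of cover. If risk is per dose, fewer doses is less exposure. This stands, and it argues against a person-time rate: equal per-dose risk gives 1/25 = 0.040 per hour after one dose and 3/48 = 0.0625 after three, which looks 36% lower with no difference in per-dose safety. It does not rescue crude counts, which cannot separate less exposure from less observation.

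**Conclusion.** The concern holds in limited form. Full adverse-event observation is about 25, 36 or 48 h according to a dose count that treatment can change, and SAP 20.2 makes no allowance for it. The likely effect on the arm comparison is small, 0 to 7.5% fewer infants with an event if surfactant shortens dosing. It rests on the protocol's ventilation figures, equal and constant hazards, and assumed pre-randomisation ventilation, lead time and event risk.

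That surfactant will look safer is only a possible direction. If it did not shorten dosing there would be no such bias, and if it lengthened dosing the bias would reverse. The point is worth correcting because the bias is avoidable at low cost. Lavage that is "repeated daily while the infant remains on MV", and so continues after 49 h, raises a separate question and does not bear on this conclusion.

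**What to change.** 1. **Protocol 8.2, 8.5, 10.7 and Table 1:** collect all adverse events in every infant from randomisation to one fixed time covering the three-dose schedule plus 24 h (49 h), regardless of doses received. Leave the longer limits for adverse reactions, serious events and named outcomes as they are.
2. **SAP 20.2:** make this fixed window the between-arm adverse-event table.
3. **Infants already treated under the present rule:** the SAP is dated April 2024, and a wording change cannot recover events that were never recorded. Add observation time by arm, adverse events by number of doses received, and a supplementary table from randomisation to 24 h. State that this table largely omits the period after the third dose (T23 to T25), that complete withdrawals may fall short of 24 h, and that it needs onset times. The documents mention only a date of onset, and only on the serious-event form (Protocol 10.8.3).
4. **Do not make events per infant-hour the main comparison**, since it misleads if risk is per dose.

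**Cost:** up to about 24 more hours (49 - 25) of non-serious event recording in infants who stop early, and one or two more tables. Daily data collection already runs to hospital discharge (Protocol 8.2), and no dosing or clinical rule changes.

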10.8 Reporting Procedures

All serious events (SAEs/SARs/SUSARs) must be reported in an expedited manner. Depending on the nature of the event the reporting procedures below should be followed. Any questions concerning adverse event reporting should be directed to the CTRC in the first instance. If a site has a serious or urgent query regarding an adverse event outside of CTRC office hours they should contact the Chief Investigator, [name], on [name].

A flowchart is given below to aid in determining reporting requirements.

IRAS 220853 Page **55** of **87**

IRAS 220853 Page **56** of **87**

IRAS 220853 Page **57** of **87**

10.8.2 Non serious events (ARs/AEs)

All non-serious events (i.e. AEs and ARs), whether expected or not, should be recorded on an "Adverse Event CRF", which should be transmitted to the CTRC within seven days of the local research team becoming aware of the event.

10.8.3 Serious events (AEs/ARs/SUSARs)

All serious events (i.e. SAEs, SARs and SUSARs) must be reported to CTRC within 24 hours of the local site becoming aware of the event. The "Serious Adverse Event CRF" asks for the nature of the event, date of onset, severity, corrective therapies given, outcome and causality. The reporting local Investigator should assign the causality of the event. Additional information should be sent within 5 days if the event has not resolved at the time of initial reporting.

All adverse events assessed as serious, related and unexpected (i.e. SUSARs) will be reported on to the MHRA and BESS's Research Ethics Committee (REC) by the CTRC according to the following timelines; fatal and life-threatening SUSARs within 7 days of notification to CTRC and non-life threatening SUSARs within 15 days. BESS PIs will be notified of all SUSARs occurring throughout the trial by the CTRC. Local Investigators should report any SUSARs and/or SAEs/SARs as required locally.

NOTE: please ensure that multiple Serious Adverse Events are reported separately to the CTRC. Each individual SAE report should relate to one overall diagnosis only.

10.9 Safety Reporting Responsibilities – Investigator

The local site Investigator (site Principal Investigator (PI)) is responsible for reporting all events that are observed or reported during the study, regardless of their relationship to study product (i.e. AEs/ARs/SAEs/SARs/SUSARs)..

All serious adverse events (SAEs/SARs/SUSARs) must be reported immediately by the investigator to the CTRC on an SAE. All non-serious adverse events should be reported to CTRC within seven days of the local research team becoming aware on an AE CRF.

Minimum information required for reporting serious events

- Valid European Clinical Trials Database (EudraCT) number (if applicable)
- Sponsor study number
- One identifiable coded subject (randomisation number)
- One identifiable reporter (name of PI or appropriate delegated individual)
- One SAE
- One suspect IMP (poractant alfa)
- A seriousness assessment
- A causality assessment

IRAS 220853 Page **58** of **87**

Process for reporting serious events

- i. The SAE CRF should be completed by a local Investigator, named on the 'signature list and delegation of responsibilities log' as responsible for reporting SAEs and making trial related medical decisions. The Investigator should assess the SAE for the likelihood that it is a response to the trial intervention. In the absence of the designated Investigator the SAE CRF should be completed and signed by an alternative member of the research site trial team and submitted to the CTRC. As soon as possible thereafter the responsible Investigator should check the SAE CRF, make amendments as appropriate, sign and re-send to the CTRC. The initial report shall be followed by detailed follow-up CRF reports as appropriate (see number vii).
- **ii.** The "Serious Adverse Event CRF" **must** be submitted to the CTRC **within 24 hours** of the local research team becoming aware of the event; preferably this will be via fax.

Email address: [contact]

[contact]

- **iii.** When submitting a SAE CRF to the CTRC research sites must also telephone the appropriate Trial Co-ordinator or Data Manager on [contact]** to advise that an SAE CRF has been submitted.
- iv. The participant **must** be identified by trial randomisation number, date of birth and initials **only**. The participant's name **must not** be used on any correspondence.
- v. The local reporting Investigator must **notify** their R&D department of the event (as per standard local governance procedures).
- vi. The participant must be followed-up until clinical recovery is complete and laboratory results have returned to normal, or until the event has stabilised. Follow-up should continue after completion of protocol treatment as necessary.
- vii. Follow-up information should be noted on a separate CRF by ticking the box marked 'follow-up' and submitting to the CTRC as information becomes available. Extra, annotated information and/or anonymised copies of test results may be provided separately.

